11.4 Notification of Adverse Events

Sponsor Notification:

The investigational center staff must report all AEs to Medtronic in a timely manner. All severe hypoglycemia, DKA, SAE, SADE, and DD with SADE potential should be reported as soon as possible (desired within 24 hours of investigator or study coordinator awareness) to Medtronic. For the previously mentioned events, the AE eCRF will be completed with all known details as soon as possible, this will serve as notification to Medtronic. If the study database cannot be accessed due to technical problems, contact the sponsor via email at [contact] and provide the de-identified known details of the event. Once the access issue has been corrected, the event should be entered onto an AE eCRF.
CIP336 Clinical Investigation Plan			
D00459338	Version E	Page 108 of 159	Medtronic

Source documents that support the event (e.g., clinic notes, hospital admission and discharge records, lab reports, EMT reports, ER/Urgent Care) should be provided to the sponsor via Medtronic's secure upload application. All source documents/medical records should be redacted of patient identifiers (full name, address, etc.) prior to providing to the sponsor. Each source page should be identified with the subject ID.

11.5 Expedited Safety Reporting Requirements

US only: For device studies, investigators are required to submit a report of a UADE to the sponsor and the reviewing IRB as soon as possible, but in no event later than 10 working days after the investigator first learns of the event (812.150(a)(1)).

US and Canada: The sponsor will notify the investigator and EC/IRB of any event that results in a safety report per regulations to the FDA/Health Canada. Documentation of EC/IRB notification of any safety event must be kept at the investigational center and a copy sent to the sponsor.

It is the responsibility of the investigator to follow their EC/IRB reporting requirements.

11.6 Adverse Event and Device Deficiency Classification

All AEs and DDs will be reviewed by sponsor and will be classified according to the responsibilities as outlined below in **Table 7**.

Upon sponsor's receipt of an event, a Safety representative will review the AE/DD for completeness and accuracy and when necessary will request clarification and/or additional information from the Investigator.

It is the responsibility of the investigator and sponsor to abide by any additional AE reporting requirements stipulated by the IRB/EC responsible for oversight of the study.

What is classified?	Who classifies?	Classification Parameters
Delatednoss	Investigator	Device, Procedure
Relatedness	Sponsor	Device, Procedure
Seriousness	Investigator	SAE, DD with SADE potential
Senousness	Sponsor	SAE, UADE/USADE, and DD with SADE potential
	Investigator	Based on presenting signs and symptoms and other
Diagnosis	Investigator	supporting data
	Sponsor	MedDRA term assigned based on the data provided by
	Эропзог	Investigator

Table 7. Adverse Event Classification Responsibilities

11.7 Causality Assessment

An AE is not automatically related to the study device or procedure simply because the subject is wearing the device and participating in the study. The event should be reviewed to determine if the device or study procedure could have possibly caused the event and therefore is related to the study device or procedure.

Causality assessment is the determination of the relationship between an AE and the device being studied. It is expected that the investigational center will review all elements surrounding the AE to properly assess the causality of the event to the study device or to a study procedure.

This review would include the subjects' description of the event, study device uploads and medical records (if applicable) from the treating facility. These records will be made available to sponsor.

Investigators should classify the relationship between the AE and the study device or study procedures using one of the four possible causality categories listed below:

- **Not related:** relationship to the device, comparator, or procedures can be excluded when:
 - the event has no temporal relationship with the use of the investigational device or the procedures related to the application of the investigational device;
 - the event does not follow a known response pattern to the medical device (if the response pattern is previously known) and is biologically implausible;
 - the discontinuation of medical device application or the reduction of the level of activation/exposure - when clinically feasible – and reintroduction of its use (or increase of the level of activation/exposure), do not impact on the event;
 - the event involves a body-site or an organ not expected to be affected by the device or procedure;

CIP336 Clinical Investigation Plan			
D00459338	Version E	Page 110 of 159	Medtronic

- the event can be attributed to another cause (e.g., an underlying or concurrent illness/ clinical condition, an effect of another device, drug, treatment or other risk factors);
- the event does not depend on a false result given by the investigational device used for diagnosis, when applicable;

In order to establish the non-relatedness, not all the criteria listed above might be met at the same time, depending on the type of device/procedures and the event.

- **Possible:** the relationship with the use of the investigational device, comparator, or the relationship with procedures, is weak but cannot be ruled out completely. Alternative causes are also possible (e.g., an underlying or concurrent illness/clinical condition or/and an effect of another device, drug or treatment). Cases where relatedness cannot be assessed, or no information has been obtained should also be classified as possible.
- **Probable**: the relationship with the use of the investigational device, comparator, or the relationship with procedures, seems relevant and/or the event cannot reasonably be explained by another cause.
- **Causal relationship:** the event is associated with the investigational device, comparator, or with procedures beyond reasonable doubt when:
 - the event is a known side effect of the product category the device belongs to or of similar devices and procedures;
 - the event has a temporal relationship with investigational device use/application or procedures;
 - the event involves a body-site or organ that
 - the investigational device or procedures are applied to;
 - the investigational device or procedures have an effect on;
 - the event follows a known response pattern to the medical device (if the response pattern is previously known);
 - the discontinuation of medical device application (or reduction of the level of activation/exposure) and reintroduction of its use (or increase of the level of activation/exposure), impact on the event (when clinically feasible);
 - other possible causes (e.g., an underlying or concurrent illness/clinical condition or/and an effect of another device, drug or treatment) have been adequately ruled out;
 - harm to the subject is due to error in use;
 - the event depends on a false result given by the investigational device used for diagnosis, when applicable;

In order to establish the relatedness, not all the criteria listed above might be met at the same time, depending on the type of device/procedures and the event.

D00459338	Version E	Page 111 of 159	Medtronic

Example: A severe hyperglycemia AE with the following event description would have the following causality assessment for device relatedness:				
Improved glucose without an infusion set/site change Not related				
Changed infusion set with glucose improvement	Possible			
Infusion set fell out, bent cannula, occlusion alarm	Causal relationship			

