5.2 Rationale

Previous clinical investigations have confirmed the safety and clinical performance of the 780G insulin pump when used to delivery Humalog or Novolog/NovoRapid U100 insulin to patients 7- 80 years of age. In-silico modeling provided in 10977370DOC (Faster Insulin Aspart [Fiasp] Compared to Insulin Aspart - In-Silico Studies with MiniMed 670G HCL) indicates that the use of Fiasp U100 insulin with the MiniMed 670G pump will result in similar outcomes to those associated with use Humalog or Novolog/NovoRapid U100 insulin. These results provide a preliminary confirmation of the safety of using Fiasp with the 780G insulin pump. This investigation is intended to provide additional confirmation of the safety of the 780G insulin pump used in combination with Fiasp U100 insulin in humans.

6. Product Description

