11.2 Definitions and Classification of Adverse Events

Medtronic uses the definitions provided in ISO 14155:2020 and 21 CFR 812 for AE definitions. Where the definition indicates "device", it refers to any device used in the study. This might be the device under investigation, or any market released component of the system.

Severe Hypoglycemia is an event requiring assistance of another person due to altered consciousness to actively administer carbohydrate, glucagon, or other resuscitative actions. This means that the subject was impaired cognitively to the point that he/she was unable to treat himself or herself, was unable to verbalize his or her needs, and was incoherent, disoriented and/or combative.

These episodes may be associated with sufficient neuroglycopenia to induce seizure or coma. Plasma glucose measurements may not be available during such an event, but neurological recovery attributable to the restoration of plasma glucose to normal is considered sufficient evidence that the event was induced by a low plasma glucose concentration.²

Severe Hyperglycemia is defined as hyperglycemia (BG greater than [>] 300 mg/dL or 16.7 mmol/L) with BG ketones greater than (>) 1.5 mmol/L, and/or accompanied by symptoms of nausea, vomiting or abdominal pain.

The meter and ketone test strips are supplied for the evaluation of ketone monitoring. Only blood ketones will be recognized (not urine ketones) for assisting in diagnosis of severe hyperglycemia. The monitors/test strips are quality controlled prior to dispensing to subjects. Blood ketones provide contemporaneous understanding of ketone levels associated with elevations in glucose.

Diabetic Ketoacidosis/DKA diagnostic criteria: BG greater than (>) 250 mg/dL or greater than (>) 13.9 mmol/L, arterial pH less than (<) 7.3, bicarbonate less than (<) 15 mEq/L, moderate ketonuria or ketonemia and requiring treatment within a health care facility.³

Hyperglycemic events will be recorded as DKA if the event includes the presence of all of the following:

- Arterial blood pH less than (<) 7.30 or serum bicarbonate less than (<) 15 mEq/L
- Blood glucose greater than (>) 250 mg/dL or greater than (>) 13.9 mmol/L
- Serum ketones or large/moderate urine ketones
- Symptoms such as polyuria, polydipsia, nausea, or vomiting
- Treatment provided in a health care facility

Adverse Event (AE) (ISO 14155:2020)

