11.3 Reporting of Adverse Events

The investigator or designee will record ALL AEs and DDs while the subject is enrolled in the clinical study (Refer to **Section 13** for DDs reporting).

Each AE needs to be assessed for its device or procedure relatedness. A device related AE is associated with the use of the study device (e.g., infection of sensor site or infusion set occlusion resulting in DKA).

CIP336 Clinical I			
D00459338	Version E	Page 107 of 159	Medtronic

A procedure related AE is associated with testing related to the study procedures specified in the CIP (e.g., needle (blood draw) insertion pain).

Examples of device or procedure related AEs include:

- **Device** related (ADE): insertion site infection
- Serious adverse *device effect*. cellulitis at device insertion site requiring hospitalization
- Procedure related AE: bruising at needle (blood draw) insertion site

Subjects participating in the study have diabetes and are expected to experience hypoglycemia and or hyperglycemia. These normal events are not expected to be reported to sponsor as this is not considered an untoward event, but rather an expected occurrence. Any glycemic excursion that meets the protocol definition of severe hypoglycemia, severe hyperglycemia or DKA is considered an untoward event and a worsening from the subject's baseline and would be reported to sponsor on an AE eCRF.

Baseline medical conditions should only be reported to sponsor on an AE eCRF if there is a worsening from the subject's baseline. For example, a subject previously diagnosed with asthma is hospitalized for severe asthma attack would be a reportable event.

Adverse events will be documented in the subject source file and reported to sponsor on an eCRF. The investigational center is responsible for documentation of AEs including obtaining source documents related to the event, such as emergency medical technician/paramedic reports, hospital records (admission summary; lab results, test results, discharge summary) or device uploads to support the event. Source documents will be reviewed to determine if additional AEs have occurred and require reporting.

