11.8 Anticipated or Unanticipated

If an AE is determined to be related to the study device the sponsor will then assess the event to determine if it is anticipated or unanticipated.

- **Anticipated:** the event is identified in the CIP; labeling; report of priors/ IB or user guide.
- **Unanticipated:** the event has not been previously identified in the CIP; labeling; report of priors/ IB or user guide.

12. Data Review Committees

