12.2 Data Monitoring Committee

A data monitoring committee (DMC) consisting of external physicians with an expertise in Endocrinology and the management of insulin-requiring diabetes including CGM, along with an external statistician will be convened to review study progress and safety. The Board will convene approximately every 90 days. The Board will also meet when ad hoc review is required.

The DMC will perform 4 main functions:

First: DMC will track and trend the overall safety of the study. Event rate, defined as number of events per 100 patient years will be reviewed by the DMC with respect to the following:

- Event rate of all SAEs
- Event rate of severe hypoglycemia
- Event rate of severe hyperglycemia
- Event rate of DKA
- Event rate of device related AEs

CIP336 Clinical Investigation Plan Medtronic D00459338 Version E Page 114 of 159

Second: Based on their meetings, DMC will recommend a decision to the sponsor regarding the following:

- Whether or not enrollment should be halted.
- Whether or not the entire study will need to be stopped including for those subjects who have received study devices already.

Note: If it is decided to withdraw subjects from participation in the study or if the study is stopped, subjects will be followed-up in accordance with standard practice by their own providers.

Third:

During the study, the following steps will be taken for:

- Unanticipated adverse device effects (UADE)
- Unanticipated Serious Adverse Device Effects (USADE)
- Device related DKA
- Device related severe hypoglycemia

DMC is to meet within 10 days from the time that the CEC adjudicates an event as one of the above. If possible, the investigator should be available to answer questions by DMC.

Based on their meeting, DMC will recommend a decision to the sponsor regarding the following:

- Whether or not enrollment should be halted.
- Whether or not the entire study will need to be stopped including for those subjects who have received study devices already.

Note: If it is decided to withdraw subjects from participation in the study or if the study is stopped, subjects will be followed-up in accordance with standard practice by their own providers.

Fourth: The DMC will review Safety data and provide a recommendation to the sponsor regarding staged enrollment of pediatric subjects:

The DMC will provide a recommendation to proceed with the following staged enrollment:

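### Adverse events are classed for relatedness to device and procedure only, so an event attributed solely to Fiasp can be coded Not related and cannot be tabulated as Fiasp-related

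*Protocol*

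**What the plan says.** Section 11.3 of the protocol: "Each AE needs to be assessed for its device or procedure relatedness". Section 11.1 gives the same two targets. Table 7 in section 11.6 gives the parameters for both investigator and sponsor as "Device, Procedure". Section 11.7 defines the exercise: "Causality assessment is the determination of the relationship between an AE and the device being studied". Where a definition in section 11.2 speaks of a device, "it refers to any device used in the study"; Table 1 lists Fiasp in a separate drug block.

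One of the grounds for Not related in section 11.7 is that "the event can be attributed to another cause (e.g., an underlying or concurrent illness/ clinical condition, an effect of another device, drug, treatment" accounts for it, and not every listed criterion has to be met.

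Later steps depend on the result. Section 11.8: "If an AE is determined to be related to the study device the sponsor will then assess the event". Sections 12.1 and 12.2 set deadlines for four kinds of event: UADE, USADE, device-related DKA and device-related severe hypoglycemia. These are FDA notice in about 72 hours (US), CEC adjudication within 10 days of sponsor notification, and then "DMC is to meet within 10 days from the time that the CEC adjudicates an event as one of the above".

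The Synopsis gives the indication under investigation as labeling for Fiasp in the 780G, and section 5.2 says the study is to provide "additional confirmation of the safety of the 780G insulin pump used in combination with Fiasp U100 insulin in humans".

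**The concern.** The insulin is what is new here: section 5.2 says the pump has already been studied with other rapid-acting insulins. The plan recognises that Fiasp carries risks. Table 6 has a row for them, and exclusion criterion 1 (section 8.4) concerns hypersensitivity to insulin aspart or the Fiasp excipients. Yet it gives no one a way to record that an event was related to Fiasp. The nearest rule points the other way, since a drug effect is a reason to code Not related.

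Two things are at stake. The safety report could not say how many adverse events were related to Fiasp. And some events attributed to the insulin alone could lose the only review deadlines that the protocol states.

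**Working it through.** This is mainly a reading of the text; the plan has no figure of its own to reproduce.

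**Step 1: is Fiasp covered by one of the two targets?** It is not a device under sections 11.2 and 6.2 (Table 1). The procedure examples in section 11.3 are blood-draw effects. So there is no target for an event attributed to Fiasp alone.

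**Step 2: does the Not related ground reach it?** A systemic allergic reaction to the insulin, with the pump, set and sensor judged uninvolved, fits a drug effect as the cause. Nothing in section 11.7 excludes the study insulin. The worked example there also codes a severe hyperglycemia that improves without a set change as Not related, without considering the insulin.

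**Step 3: what follows for an event attributed only to Fiasp and coded Not related?**

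| Step | Depends on device relatedness? | Result |
|---|---|---|
| Anticipated/unanticipated (11.8) | Yes | Not assessed |
| US FDA notice, about 72 h (12.1) | Yes, or UADE/USADE | Not triggered |
| CEC within 10 days (12.1) | Yes, or UADE/USADE | No stated deadline |
| DMC within 10 days of adjudication (12.2) | Yes, or UADE/USADE | Not triggered |
| DMC rate of device-related AEs (12.2) | Yes | Not counted |
| CEC review of SAE, severe hypoglycemia, DKA, severe hyperglycemia (12.1) | No | Still reviewed |
| DMC rates of those four (12.2) | No | Still counted |

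A non-serious, non-glycemic event reaches neither of the last two rows, so it is not tracked at committee level. UADE and USADE do not rescue a Fiasp-only event, because section 11.2 defines both by a link to a device.

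**Step 4: the clocks.** With the trigger, the longest time from sponsor notification to a DMC meeting is 10 + 10 = 20 days. Without it there is no deadline, and the scheduled interval is about 90 days, roughly one subject's whole study period. The worst-case difference is 90 − 20 = 70 days if no ad hoc meeting is called.

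**Step 5: exposure, for scale.** If 200 subjects enter the study period for 90 days each, Fiasp exposure is 200 × 90 / 365.25 = 49.3 patient-years. Enrollment of ages 7–17 can open once 10 adults have completed 30 days and the DMC agrees. Those adults contribute 10 × 30 / 365.25 = 0.82 patient-years, where a single event gives 1 / 0.82 × 100 ≈ 122 per 100 patient-years. The highest severe hypoglycemia reference rate in Table 8 is 20.9. Rates say little at that size, so the attribution of individual events carries more weight.

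**Step 6: the safety tables.** The lists in protocol section 14.5.4 and SAP sections 7.9.7 and 7.10 contain no Fiasp-related category, and no required classification would supply one.

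**The case against.** The case on the other side is substantial, and most of it stands.

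- **Coding is permissive.** Section 11.7 says when a relationship can be excluded, not when it must be. Possible covers cases where a drug is an alternative cause and the device link cannot be ruled out, and it is the default when relatedness cannot be assessed. A reader might infer that all harm from Fiasp will be coded unrelated. The documents do not support that.
- **Many insulin effects keep a device route.** Section 10.4 frames the main Fiasp hazard as the closed-loop algorithm not holding control. Table 6 lists hypoglycemia under SmartGuard and closed-loop use, and irritation and rash under infusion sets. An event at the body site where the device is applied counts towards relatedness.
- **Oversight is not bypassed.** A reader might also infer that such events escape review. They do not. Sites report severe hypoglycemia, DKA and SAEs promptly whatever the cause (section 11.4). The sponsor classifies relatedness too. The CEC receives every SAE, severe hypoglycemia, DKA and severe hyperglycemia, its adjudication is used for analysis, and it may weigh factors beyond its list. The DMC clock runs from CEC adjudication, not site coding, and the DMC can meet ad hoc.
- **The objective is the system used with Fiasp, under device rules.** The primary safety endpoint is HbA1c change, and the main safety summaries do not filter on relatedness.
- **The information is recoverable.** All AEs are recorded with diagnosis, dates and description.

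What remains is that the CEC assesses agreement with a classification that has no Fiasp option, its listed considerations never name the insulin, and its 10-day clock is stated only for the trigger list. Ad hoc review is available but not required for these events.

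**Conclusion.** The gap is real and narrow. Events attributed solely to Fiasp can be coded Not related, are then absent from the DMC's device-related rate, and cannot be tabulated as Fiasp-related. The clearest cases are systemic hypersensitivity and other non-serious, non-glycemic events. A severe hypoglycemia or DKA attributed only to Fiasp can lose the 72-hour and 10 + 10 day steps while keeping CEC review and a place in the overall rates.

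The number of affected events cannot be derived from the documents. The 49.3 patient-years is total exposure and should not be read as a measure of misclassification; the 70-day difference is a worst case. Endpoints, hypothesis tests and sample size are unaffected, so this is a cheap improvement to safety coding and not a defect that undermines the trial.

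Two assumptions: sites read the drug ground as including the study insulin, which the wording permits but does not compel; and the AE eCRF, held under separate cover (section 16.3.1), has no Fiasp field beyond what Table 7 requires.

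**What to change.** - Add relatedness to Fiasp, alone or in combination with the pump, as a third target in sections 11.1, 11.3 and 11.7, Table 7 and the AE eCRF, for events with onset from Visit 7.
- State in section 11.7 that the other-drug or treatment ground excludes the study insulin.
- Key the trigger lists in sections 12.1 and 12.2, and the DMC's related-event rate, to device- or Fiasp-related events.
- Name the insulin among the CEC considerations in section 12.1.
- Add Fiasp-related AEs to the summaries in protocol section 14.5.4 and SAP sections 7.9.7 and 7.10.

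The cost is one form field, a wording amendment, short site retraining and recoding of events already entered. The downside is a few more ad hoc reviews.

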 Insulin deterioration leading to hyperglycemia Incomplete priming; fails to prime tubing and/or cannula, leading to hyperglycemia Remove a reservoir, without suspending and reconnecting after a while resulting in a hypoglycemia Patient not filling pump reservoir when needed leading to hyperglycemia Magnetic resonance imaging resulting in pump transmitter malfunction Inaccurate insulin delivery due to sudden altitude changes. Hypoglycemia or hyperglycemia from manual bolus Hypoglycemia or hyperglycemia from the use of the SmartGuard feature where SG values may be used to calculate insulin bolus amounts Hypoglycemia or hyperglycemia from computer hacking Risks with hyperglycemia may include Diabetic ketoacidosis Symptomatic ketosis Cardiovascular event Dehydration 	 Prevention and mitigation include: Follow the provided user guides for insulin pump management. Parent(s)/guardian(s)/companion(s) should be present at night with subjects. Parent(s)/guardian(s) will be trained on study device and diabetes management principles and instructed to call investigator with problems.
 Potassium and sodium imbalance Shock Altered mental status Coma Acidosis 	 Companions will be trained on diabetes management principles and emergency response training. Parent/caregivers and companions should also be present during meal and exercise challenges. Train prior to study device use on appropriate device use and diabetes management principles and instruct to call investigator with problems. Instruct to check their meter glucose if their high symptoms do not match their sensor alerts or SG readings in order to make diabetes treatment decisions.
	 Instruct to check their meter glucose if there are any concerns that the SG value is not accurate. Alternative method of managing glucose levels will be available (insulin and syringe for example).

CIP336 Clinical Investigation	
D00459338 Version E	Page 97 of 159 Medtronic

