- Subject clarification to investigational center regarding details about the event

• Source documents that support event: Paramedic records; ER records; Lab records; Hospital admission and discharge summary

The following factors should be carefully considered in the CEC's recommendation to sponsor:

CIP336 Clinical Investigation Plan			
D00459338	Version E	Page 113 of 159	Medtronic

- 1. Was the severe hypoglycemia or DKA related to the AHCL algorithm, or was it related to a known insulin pump risk? For example, a question that may be considered in DKA would be whether the event was related to an infusion set issue or caused by the AHCL algorithm.
- Another important consideration would be if the severe hypoglycemia, severe hyperglycemia or DKA event was related to a device malfunction versus patient non-compliance. For example, if a software anomaly leading to an under-delivery of insulin is discovered versus the subject repeatedly ignoring alarms prompting the subject to take action.
- 3. Severe hypoglycemia, severe hyperglycemia or DKA caused directly by an infusion set issue when the study pump is functioning as intended would likely result in acceptance to proceed with the study versus severe hypoglycemia or DKA that are directly caused by the AHCL algorithm or a device malfunction might stop study enrollment or entire study altogether.
- 4. It should be noted that the final determination of causality related to 780G system that is made by the CEC may include additional factors which the members consider to be clinically relevant and important.

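### The causality example in Protocol 11.7 scores severe hyperglycemia as not device-related on one infusion-set fact, against the protocol's own definitions, and can bias the investigator's first classification

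*Protocol*

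**What the plan says.** Protocol 11.7 gives investigators four causality categories and closes with a three-row table. It is introduced as "Example: A severe hyperglycemia AE with the following event description would have the following causality assessment for device relatedness". The first row reads "Improved glucose without an infusion set/site change Not related". The second row scores improvement after a set change as *Possible*. The third scores a set that fell out, a bent cannula or an occlusion alarm as a causal relationship. All three rows concern the infusion set.

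The text above the table is broader. On the evidence to weigh: "It is expected that the investigational center will review all elements surrounding the AE to properly assess the causality", and "This review would include the subjects' description of the event, study device uploads and medical records". On doubtful cases: "Cases where relatedness cannot be assessed, or no information has been obtained should also be classified as possible". Among the criteria for a causal relationship: "the event depends on a false result given by the investigational device used for diagnosis, when applicable".

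Protocol 11.2 defines device as any device used in the study. Table 6 (Section 10.1) lists, among the device risks, "Hypoglycemia or hyperglycemia from the use of the SmartGuard feature where SG values may be used to calculate insulin bolus amounts". Its closed-loop part adds hyperglycemia from sensor under-reading and from missed sensor transmissions.

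**The concern.** The example treats one negative finding about one component as excluding the whole system. A SmartGuard under-delivery or a sensor under-reading can be corrected by a bolus or by recovery of the sensor signal, with the infusion set left in place. Such an event fits the first row exactly, and a site following the row would score it *Not related*.

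This matters because Protocol 10.4 names, as a theoretical risk, that the closed-loop algorithm may not hold glucose control with Fiasp as well as with other insulins. The example has no row for that failure mode. What is at stake is the investigator's first relatedness score and what depends on it before adjudication: the device-related adverse event rate listed for the DMC in 12.2, and the sponsor's anticipated or unanticipated assessment in 11.8, which begins only once an event is judged related.

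**Working it through.** The plan states no figure here, so the main check sets the passages side by side.

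1. *The row against the 11.7 definitions.* *Not related* requires that a relationship can be excluded. Improvement without a set change argues against a set failure; it says nothing about the algorithm, pump delivery or the sensor. *Possible* covers a weak link that cannot be ruled out, and also cases that cannot be assessed. If the pump and sensor upload has not been examined, the row's single fact does not meet the exclusion standard.
2. *The row against 11.2 and Table 6.* Device means the full system. Table 6 names SmartGuard dosing from sensor values, sensor under-reading and missed transmissions as routes to hyperglycemia. None of them needs a set change to resolve.
3. *The row against 12.1.* The CEC's second factor covers severe hyperglycemia and contrasts device malfunction with non-compliance: "if a software anomaly leading to an under-delivery of insulin is discovered versus the subject repeatedly ignoring alarms". The protocol therefore recognises a software route that the example leaves out.
4. *What corrects the first score.* Table 7 has the sponsor classify relatedness too. Under 12.1 the CEC reviews severe hyperglycemia reports with no relatedness filter, and its adjudication is the one used for data analysis.
5. *Where that correction is incomplete.*
   - The CEC's review of sensor and pump reports is optional and worded for device-related events.
   - Its first factor, on algorithm causation, names severe hypoglycemia and diabetic ketoacidosis (DKA) but not severe hyperglycemia.
   - The 12.1 list that triggers rapid notification and a 10-day adjudication includes device-related DKA and device-related severe hypoglycemia, but not device-related severe hyperglycemia. The ad hoc DMC list in 12.2 has the same gap, and no other adjudication deadline is stated.
   - Section 12.2 does not say which classification feeds the device-related rate before adjudication.
6. *Outputs that do not depend on relatedness.* The DMC also sees the rate of all severe hyperglycemia (12.2), and SAP 7.9.7 and 7.10 summarise its incidence. The pass/fail criteria (Protocol 14.5.2.1, SAP 7.9.1) rest on HbA1c and CGM-based effectiveness endpoints.

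Scale only. Inputs: 71.64 severe hyperglycemia events per 100 patient-years (Table 8, under-15 column; the older columns give no rate), 100 to 125 pediatric subjects (Protocol 8.1) and about 90 days of study period (Section 5). Assumption: the under-15 rate holds for everyone aged 7 to 17.

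Events = subjects × (90/365) × 0.7164

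- 100 subjects: 24.7 patient-years × 0.7164 = 17.7 events
- 125 subjects: 30.8 patient-years × 0.7164 = 22.1 events

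The documents do not give the share that improves without a set change, the share of those with an algorithm or sensor cause, or the share the CEC would reverse. The calculation stops at total events.

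**The case against.** The strongest reply is that the table is labelled an example and guides only the first score. The governing text in the same section tells sites to use device uploads, and a site that sees under-delivery or a sensor error there has the definitions it needs to score *Possible* or higher. The sponsor classifies separately, and the CEC's decision overrides the investigator's in the analysis. *Not related* may properly rest on another cause, such as illness or a missed bolus, and not every criterion has to be met. Section 12.1 also lists CareLink report review among the information that events in general may need, and its fourth factor allows the CEC to weigh anything clinically relevant.

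Most of this stands. A reader might infer that algorithm and sensor events are removed from the device-related count, or that a particular number of events is misclassified by rule. The documents support neither: the investigator's score is not final, many events that improve without a set change will be correctly unrelated, and the number wrongly scored and left uncorrected could be zero. Nor can a lowered summary of adverse device effects be claimed, since the SAP's visible safety lists name only serious and unanticipated device effects.

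The reply does not rescue the row itself. It states the assessment such an event would have, on a fact that does not meet the definition above it. The CEC safeguard is also least explicit for this event type: the algorithm factor omits severe hyperglycemia, and the specific pump and sensor review is worded for events already called device-related.

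**Conclusion.** The row is inconsistent with Protocol 11.2, 11.7 and Table 6 and should be changed. Its effect is a possible bias of the investigator's initial classification toward *Not related*. Unless and until the CEC reverses the score, this could lower the device-related adverse event rate the DMC may see. That rests on some sites applying the row as written and on unadjudicated scores reaching the DMC; the documents neither confirm nor exclude either. Total severe hyperglycemia incidence, the primary endpoints and the pass/fail criteria are untouched.

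The number of misclassified events cannot be derived. The figure of about 18 to 22 pediatric events in 90 days shows only how many severe hyperglycemia events might need a relatedness score, under the assumption about the reference rate. Table 8 gives no corresponding adult rate.

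**What to change.** In Protocol 11.7:

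- Reword the first row so that improvement without a set or site change is *Not related* only when the pump and CGM upload has been reviewed, shows no evidence of an algorithm, delivery or sensor cause, and the event is attributed to another cause. Otherwise it is *Possible*. Time outside SmartGuard should not by itself block *Not related*, because Section 5 anticipates such periods.
- Add a row illustrating an algorithm or sensor cause.

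In Protocol 12.1:

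- Add severe hyperglycemia to the CEC's first factor, on algorithm causation.
- State that the CEC's sensor and pump data review applies to all severe hyperglycemia, whatever relatedness score the investigator gave.

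No separate re-adjudication is needed, because the CEC already reviews these events. The cost is protocol wording and a memo to sites, using uploads already collected. The one small downside is that the device-related adverse event rate may rise slightly.
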